# **Population:**

This study will use the US-based Optum's Electronic Health Record (EHR) data, with supplemental linkage to Optum's Integrated Claims-Clinical adjudicated claims dataset for those patients in the EHR who also have claims data available. For a subset of patients in the EHR, patient electronic clinical notes exist which will allow manual clinician review at Optum to confirm myocarditis cases based on available data that align with the Brighton Collaboration criteria. The proposed study period is 01 January 2010 to most recent available at the time of start of data collection (31 March 2023)), to allow sufficient baseline time to examine risk factors for patients with myocarditis in each of the three cohorts, with index dates of 2016-later.

Among the overall Optum EHR study population of all ages, the following mutually exclusive cohorts and index dates will be defined to address the study objectives:

- Cohort 1 Post-mRNA COVID-19 vaccination myocarditis cohort: first date of a
  myocarditis diagnosis code within 21 days after vaccination from 11 December 2020 to most
  recent data available, allowing for at least 30 days pre or post index for medical notes to
  confirm diagnosis through end of study period.
- Cohort 2 Post-SARS-CoV-2 infection myocarditis: first date of a myocarditis diagnosis
  code within 8 weeks after a positive SARS-Cov-2 test from 01 January 2020 to most recent
  data available, allowing for at least 30 days pre or post index for medical notes to confirm
  diagnosis through end of study period.
- Cohort 3 Pre-COVID myocarditis: most recent date of a myocarditis diagnosis from 01 January 2016 to 01 November 2019, allowing for at least 30 days pre or post index for medical notes to confirm diagnosis through end of study period.
- Controls for the multivariable risk factor analysis, a random sample of matched patients without myocarditis will be selected, e.g. with an encounter date during the same month as the index date for the myocarditis case, and with a similar amount of follow-up time from entry into the cohort and activity in the database. Additional matching criteria may be

determined, and details of the matching methods and appropriate modeling considerations will be provided in the statistical analysis plan (SAP).

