# 8. RESEARCH QUESTION AND OBJECTIVES

The objective of this study is to characterize risk factors for myocarditis in the following three cohorts: 1) myocarditis diagnosed post any type of mRNA COVID-19 vaccine, 2) myocarditis diagnosed post SARS-CoV-2 infection (2020-2022), or 3) myocarditis diagnosed prior to the COVID-19 era (pre-2020). To accomplish this objective, the study will characterize demographics, medical history, and comorbidities of patients with myocarditis prior to diagnosis during a baseline period and then examine risk factors for myocarditis using multivariable models. Myocarditis cases identified in the EHR or claims post-vaccine or post COVID-19 infection, as well as a sample of cases in the pre COVID era cohort, will be validated by clinicians using the Brighton Collaboration criteria  applied to review of medical records at Optum as the gold standard. Using those validated cases, the study will also assess and compare the PPV for the myocarditis definitions based on codes for the three cohorts in the Optum deidentified EHR data.

Among patients diagnosed with myocarditis in the deidentified Optum EHR data, the study specific objectives are detailed below.

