#### 9. RESEARCH METHODS

#### 9.1. Study design

This is a NI, observational, retrospective cohort study utilizing a nested case-control design with secondary data collection. The broader cohort for this study is the Optum EHR database during the proposed study period of 01 January 2010 to most recent available at the time of start of data

[figure not shown]
collection (31 March 2023). This study period has been chosen to reflect the most current and complete data in the Optum database, with sufficient baseline time to examine risk factors for patients with myocarditis in each of the cohorts with index dates of 2016-later.

**Figure 1** summarizes the overall study design. Among the overall Optum EHR study population, the following mutually exclusive cohorts and index dates will be defined to address the study objectives:

- Cohort 1 Post-mRNA COVID-19 vaccination myocarditis cohort: first date of a
  myocarditis diagnosis code within 21 days after vaccination from 11 December 2020 to most
  recent data available, allowing for at least 30 days pre or post index myocarditis diagnosis for
  medical notes to confirm diagnosis through end of study period.
- Cohort 2 Post-SARS-CoV-2 infection myocarditis: first date of a myocarditis diagnosis code within 8 weeks after a positive SARS-CoV-2 test from 01 January 2020 to most recent data available, allowing for at least 30 days pre or post index myocarditis diagnosis for medical notes to confirm diagnosis through end of study period.
- Cohort 3 Pre-COVID myocarditis: most recent date of a myocarditis diagnosis from 01 January 2016 to 01 November 2019, allowing for at least 30 days pre or post index myocarditis diagnosis for medical notes to confirm diagnosis through end of study period.
- Controls for the multivariable risk factor analysis, a random sample of matched patients
  without myocarditis will be selected, e.g. with an encounter date within the same month as
  the index date for the myocarditis case, and with a similar amount of follow-up time from
  entry into the cohort and activity in the database. Additional matching criteria may be
  determined, and details of the matching methods and appropriate modeling considerations
  will be provided in the SAP.

Additional details on index dates and episode definitions will be provided in the SAP.

Figure 1. Study Design

- Censored at minimum of myocarditis diagnosis, death, disenrollment, or end of the study period

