# **Myocarditis cases:**

- 2. Diagnosis of myocarditis identified using ICD codes in EHR and/or claims when available. (ICD codes will be provided in the SAP)
- 3. At least one myocarditis inpatient record or two myocarditis records of any type dated greater than or equal to 30 days apart
- 4. Myocarditis diagnosis date between 01 January 2016 most recent EHR data available (31 March 2023)
- 5. At least 365 days of enrollment or activity in the EHR prior to the index myocarditis diagnosis.

Myocarditis cases meeting the above criteria will be divided into the following three cohorts with their own unique inclusion criteria:

- a) Cohort 1 Post- mRNA COVID-19 vaccine myocarditis cases:
  - 1. Myocarditis diagnosis date 11 December 2020 or later
  - 2. Record of mRNA vaccination within 21 days prior to the myocarditis diagnosis without a record of SARS-CoV-2 positive test within 8 weeks prior to myocarditis diagnosis
  - 3. Availability of medical notes to use for confirmation of myocarditis post-mRNA COVID-19 vaccination thirty days before or after the index event
- b) Cohort 2 Post- SARS-CoV-2 infection myocarditis cases:
  - 1. Myocarditis diagnosis date 01 January 2020 or later
  - 2. Record of SARS-CoV-2 positive test within 8 weeks prior to myocarditis diagnosis, with no record of mRNA COVID-19 vaccination during that time
  - 3. Availability of medical notes to use for confirmation of myocarditis post-SARS-CoV-2 infection thirty days before or after the index event
- c) Cohort 3 Pre-COVID-19-era acute/viral myocarditis cases:
  - 1. Most recent Myocarditis diagnosis date prior to 01 November 2019
  - 2. Availability of medical notes to use for confirmation of myocarditis within thirty days before or after the index event

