myocarditis. Laboratory results and vital signs/other biometric measures may be incomplete and therefore only available for a subset of the patients. Another limitation inherent to EHR databases is that information on prescriptions recorded for outpatients in this database does not necessarily indicate that the medication was consumed or taken as prescribed; similarly, medications filled over the counter or provided as samples by the physician may not be recorded in the database. Vaccine administrations or SARS-CoV-2 infections may not be recorded in the EHR, and so myocarditis after vaccination or COVID-19 infection may be missed. Similarly, due to the nature of EHR data, conditions not requiring treatment or office visits tend to be systematically under-recorded; therefore, it is possible that this study may only capture severe conditions that are considered in the risk factor models. Patients may have received health care outside of the network of providers and healthcare organizations that contribute to the Optum databases, or prior to having the index diagnosis and we may not be able to exclude the possibility that a patient was diagnosed with myocarditis, as well as other risk factors, prior to entry into a healthcare system where Optum has EHR access. Furthermore, if observed results using ICD-9 codes significantly differ from observed results using ICD-10 codes as a result of Centers for Medicare & Medicaid Services (CMS) and the National Center for Health Statistics (NCHS) ICD-9 to ICD-10 transition, we may modify our definitions as necessary.

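### Cohort 1 is cleared of recent SARS-CoV-2 infection only by the absence of a recorded positive test, so a recently vaccinated case with a COVID-19 diagnosis code but no test record is counted as post-vaccine myocarditis

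*Protocol*

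**What the plan says.** The Cohort 1 criteria in section 9.2.1 require a "Record of mRNA vaccination within 21 days prior to the myocarditis diagnosis", and admit the case only "without a record of SARS-CoV-2 positive test within 8 weeks prior to myocarditis diagnosis". Cohort 2 is the mirror image: "Record of SARS-CoV-2 positive test within 8 weeks prior to myocarditis diagnosis, with no record of mRNA COVID-19 vaccination during that time". Section 9.1 words Cohort 2 in the same way ("first date of a myocarditis diagnosis code within 8 weeks after a positive SARS-CoV-2 test from 01 January 2020"), and so does the Population paragraph of the abstract. Nowhere does the protocol accept a COVID-19 diagnosis code as evidence of infection.

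Four other places bear on this:
- The objectives in section 8 and the exposure row of Table 1 speak of infection, not of a positive test.
- Section 9.4 says structured diagnosis data are extracted. Section 9.2.1 finds myocarditis itself from ICD codes in the EHR and, where available, claims.
- Section 9.9 describes laboratory and microbiology data as available for a subset of patients. It also concedes that "Vaccine administrations or SARS-CoV-2 infections may not be recorded in the EHR", but draws only the consequence that cases may be missed.
- Sections 9.6 and 9.8 describe the clinician review as deciding whether the notes support myocarditis under the Brighton criteria, with each case ending as validated or not validated.

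**The concern.** One rule serves two opposite purposes. For entry to Cohort 2, specificity matters, and a recorded positive test is a reasonable requirement. For clearing Cohort 1 of infection, sensitivity matters: each infection the rule fails to see leaves a possibly infection-related case labelled post-vaccine. Here the rule rests on a data element that the protocol itself calls incomplete, while a second source, the coded diagnosis, is on hand and not used.

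The primary objective compares risk factors between the myocarditis cohorts. Infection-related cases inside Cohort 1 make its odds ratios look more like those of Cohort 2 and so blur that contrast. The effect falls on the smallest cohort: about 240 cases against 1,730 in Cohort 2 (section 9.5). No described step would undo it. The note review confirms or rejects myocarditis but does not reassign a cohort on infection status, and section 9.7 also runs the models on all code-identified cases.

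**Working it through.** **Step 1: apply the criteria.** Take a myocarditis case from December 2020 or later that meets the general criteria, has usable notes, and has a COVID-19 diagnosis code in the prior 8 weeks but no positive-test record.

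| mRNA dose | Cohort 1 | Cohort 2 | Result |
|---|---|---|---|
| Within 21 days | Meets criterion 2 | Fails: no test record, and vaccinated | Counted as post-vaccine |
| None, or more than 21 days before | Fails: no dose in window | Fails: no test record | In no cohort, since Cohort 3 ends before 01 November 2019 |

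A case with the same dose and a recorded positive test within the 8 weeks is in neither Cohort 1 nor Cohort 2. The protocol thus means to keep vaccinated cases with recent infection out of Cohort 1, and the test-only wording achieves this only in part.

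**Step 2: illustrative size.** The protocol has no figure to reproduce here. It gives 240 and 1,730 as database counts and states no sample size calculation.

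Inputs:
- *i*, share of vaccinees infected within an 8-week period: 1% to 4% (assumed).
- *u*, share of infections coded but without a test record: 10% to 40% (assumed).
- *r*, myocarditis risk after infection: 5.4 to 57.2 per 100,000 within 7 days (section 7, lowest and highest subgroup).
- *v*, vaccine-related cases: 2 to 10 per 100,000 doses (assumed; section 7 gives an excess below 1 per 10,000 for the highest-risk group).
- Window factor 21/56 = 0.375. Cohort 1 counts myocarditis only in the 21 days after a dose, whereas *i* covers 56 days. At a constant infection rate, 0.375 of the events fall in the window.

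Formula: *c* = *i* × *u* × *r* × 0.375, and infection-related share of Cohort 1 = *c* / (*c* + *v*).

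| *i* | *u* | *r* | *v* | *c* | Share | Of 240 |
|---|---|---|---|---|---|---|
| 0.01 | 0.1 | 57.2 | 10 | 0.021 | 0.2% | 0.5 |
| 0.04 | 0.4 | 5.4 | 2 | 0.032 | 1.6% | 3.8 |
| 0.02 | 0.2 | 57.2 | 2 | 0.086 | 4.1% | 9.9 |
| 0.04 | 0.4 | 57.2 | 2 | 0.343 | 14.6% | 35 |

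The last row takes the unfavourable end of every input. It also pairs the infection risk of one subgroup (men aged 30 or older) with the lowest assumed vaccine rate.

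Two things could raise the share. One is a risk that lasts beyond 7 days. The other is the larger figures also quoted in section 7 (1,100 and 1,000 to 4,000 per 100,000). Those are not used because they come without a risk window, and the protocol calls the second higher than most other reports.

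**Step 3: effect on an odds ratio.** Assume a factor with 20% prevalence in controls, a true odds ratio of 1.0 after vaccination, and 2.0 or 3.0 after infection. Prevalence among infection-related cases is then 0.333 or 0.429. With contamination *q*, prevalence in Cohort 1 is (1 − *q*) × 0.20 + *q* × 0.333 (or 0.429), and its odds are divided by the control odds of 0.25.

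- *q* = 5%: 0.2067 or 0.2114, odds ratio 1.04 or 1.07.
- *q* = 10%: 0.2133 or 0.2229, odds ratio 1.09 or 1.15.
- *q* = 15%: 0.2200 or 0.2343, odds ratio 1.13 or 1.22.

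**The case against.** The strongest reply is that test-confirmed infection is a coherent, specific definition, used consistently in the abstract and in sections 9.1 and 9.2.1. Section 9.9 warns, in the context of myocarditis, that diagnosis codes may be wrong or reflect a rule-out. A COVID-19 code could behave in the same way, so adding codes would bring uninfected cases into Cohort 2 and remove true post-vaccine cases from Cohort 1. For Cohort 2 this stands: test-only is a defensible primary definition. For the Cohort 1 exclusion it stands only as a cost, because there the damage comes from infections not seen.

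A second reply is that codes and operational criteria are left to the SAP, which is not shown and might read a test record broadly, for instance to include a positive test written in a note. This stands in part. The protocol does not confine the record to an in-network laboratory, so a reader should not infer that the place of testing by itself decides the cohort. But the choice of a test over a diagnosis is already fixed in the protocol text.

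A third reply is that section 9.9 discloses unrecorded infections. It does so for missed cases, not for infected cases entering Cohort 1.

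A reader might also infer that Cohort 2 is badly depleted. For example, 1,730 × *u* / (1 − *u*) gives 192 missed cases at *u* = 10% and 1,153 at 40%. The documents do not support this, because section 9.5 does not say that the 1,730 were identified by test alone. Nor do they establish that test-only selection makes healthcare utilisation appear as a risk factor. A coded diagnosis also needs an encounter, prior utilisation is a planned covariate, and controls are to be matched on similar database activity.

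**Conclusion.** The point holds for the Cohort 1 exclusion. As written, a case vaccinated within 21 days that has a coded but untested COVID-19 diagnosis is counted as post-vaccine myocarditis, and nothing later in the protocol corrects or discloses this.

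The size cannot be derived from the documents. With *i*, *u* and *v* assumed, contamination runs from about 0.2% to 15% of Cohort 1, and a middle case gives about 4% (10 of 240). At around 5%, a true odds ratio of 1.0 would read as 1.04 to 1.07, given odds ratios of 2 to 3 after infection. That is modest, but it works towards making the two cohorts look alike. A reader might reach 31% by leaving out the window factor (0.915 / 2.915), but that applies an 8-week infected share to a 21-day window. This is a cheap and worthwhile improvement, not a flaw that invalidates the comparison.

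**What to change.** - **Section 9.2.1, Cohort 1 criterion 2:** exclude any case with a positive SARS-CoV-2 test or a COVID-19 diagnosis code, in the EHR or claims, within 8 weeks before the myocarditis diagnosis.
- **Cohort 2:** keep the test-only definition as primary and add a test-or-code definition as a sensitivity analysis.
- **Section 9.9:** state that an infection without a test record can place a case in Cohort 1, not only cause a case to be missed.

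The cost is one code list and the wording changes, using diagnosis data already extracted. Some true post-vaccine cases will be lost. If infection and vaccine myocarditis are independent, code-only infections account for *i* × *u* = 0.1% to 1.6% of them, at most about 4 of 240. Rule-out codes would add a number that the documents do not give. Reporting how many cases the added code criterion removes would show the actual size of the problem.

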- Controls risk-set matched on e.g. month/year of cohort entry, duration of follow up (from cohort entry), integrated delivery network (IDN). Matching criteria will be detailed in the SAP.
- Timeframe for each myocarditis sub-cohort:
  - 1) Post-vaccination myocarditis: December 11, 2020 November 01, 2022
  - 2) Post-SARS-CoV-2 myocarditis: January 01, 2020 November 01, 2022
  - 3) Pre-COVID era myocarditis: January 01, 2016 November 01, 2019

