# Controls for risk factor analysis:

- 1. Medical encounter and during the same month as their matched myocarditis case (index date for control select date closest to matched myocarditis case if ≥1 date/encounters are present)
- 2. At least 365 days of enrollment or activity in the EHR prior to index
- 3. No evidence of myocarditis prior to the index date
- 4. Details of matching criteria will be provided in the SAP

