#### 9.3. Variables

As described above, patients in the myocarditis cohorts will be identified via ICD codes in the EHR data, and a subset will be confirmed using Brighton Collaboration criteria  and medical record review. The main study variables of interest, including demographics, diagnostic, therapeutic and laboratory/examinations are listed in **Table 1: Variables and associated roles.** Operational definitions, codes, more detailed listings of comorbidities, procedures and treatments, as well as any additional variables will be provided in the SAP.

Table 1. Variables and Associated Roles (Detailed Operationalization to be Described in SAP)

Variable	Role
Year of birth	Demographic
Sex	Demographic
Race/Ethnicity	Demographic
Geographic region (census regions)	Demographic
Payer type	Demographic
Date of matched encounter (index date for controls)	Index
Date of qualifying myocarditis diagnosis (index date for cases)	Diagnosis and index
Age at time of diagnosis (e.g., index date, or if unavailable then age entered or calculated in database closest to myocarditis diagnosis)	Diagnosis

Variable	Role
Time to diagnosis (time from first Optum EHR record until first myocarditis diagnosis date)	Diagnosis
Time since diagnosis (time from first myocarditis diagnosis date until last date in the Optum EHR or date of death)	Diagnosis
Laboratory biomarkers if feasible (e.g. troponin, CRP, CK-MB, CPK, additional lab markers TBD)	Diagnosis
Imaging* (e.g. echocardiogram, Cardiac MRI, Cardiac Magnetic Resonance, cMR, ECG)	Diagnosis
Procedures* (Biopsy / cardiac biopsy)	Diagnosis
mRNA COVID-19 vaccination	Exposure
SARS-CoV-2 infection	Exposure
Medical comorbidities prior to diagnosis/index date** (e.g. Charlson categories, Feudtner Complex chronic conditions [CCC] for pediatric populations, Healthcare Cost and Utilization Project Clinical Classifications Software [HCUP CCS] groups, incl. cardiac, immune, inflammatory conditions)	Medical history
Treatments prior to diagnosis/index date* (e.g. prior cardiac or COVID-related treatments, frequency of other drug classes)	Medical history
Procedures prior to diagnosis/index date* (e.g. cardiac, HCUP CCS groups)	Medical history
Labs of interest prior to diagnosis/index date* (e.g. labs mentioned above, as well as other cardiac labs, basic metabolic panel, complete blood count, urinalysis, thyroid test, lipid panel, cultures)	Medical history

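### Section 9.2.1 excludes recent vaccination from Cohort 2 cases and recent infection from Cohort 1 cases, but applies neither exclusion to their controls

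*Protocol*

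**What the plan says.** Protocol Section 9.2.1, under the heading for myocarditis cases, defines each COVID-era cohort by one exposure and excludes the other.

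- Cohort 2, second criterion: a positive test on record in the 8 weeks before the diagnosis, "with no record of mRNA COVID-19 vaccination during that time".
- Cohort 1, second criterion: "Record of mRNA vaccination within 21 days prior to the myocarditis diagnosis", and no positive SARS-CoV-2 test on record in the 8 weeks before it.

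The control criteria in the same section are an encounter in the case's month, 365 days of prior activity, and "No evidence of myocarditis prior to the index date". The fourth item reads "Details of matching criteria will be provided in the SAP". None of them concerns vaccination or infection.

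The matching examples in Section 9.1 and the notes to Figure 1 are encounter month, month and year of cohort entry, length of follow-up, database activity and delivery network. Neither exposure is among them, and further matching criteria are left open.

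Table 1 (Section 9.3) gives both "mRNA COVID-19 vaccination" and SARS-CoV-2 infection the role of exposure. The Abstract says exposure variables include potential risk factors. Section 9.7 plans odds ratios for demographic and clinical characteristics and for factors picked by stepwise selection or univariate significance.

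**The concern.** In a nested case-control study, a control should be someone who would have been counted as a case had myocarditis occurred at the index date. A patient vaccinated three weeks before index could not have become a Cohort 2 case. A patient who tested positive three weeks before index could not have become a Cohort 1 case. As written, both can serve as controls.

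The case-control contrast then partly reflects the exclusion rule. The excluded exposure is absent from cases by definition and present in some controls. Characteristics that go with recent vaccination or recent infection, such as age, comorbidity, payer and utilisation, can carry part of that difference. These are the candidate risk factors of the primary objective, and univariate screening would tend to favour any factor separated in this way.

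This point concerns the other exposure in each cohort. It would remain even if controls were required to share the cohort-defining exposure.

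**Working it through.** The protocol states no odds ratio or power figure to reproduce. The check sets the eligibility rules side by side and then works out their effect when the true odds ratio is 1.

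**Eligibility**

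| Condition before index | Cohort 1 cases | Cohort 2 cases | Controls |
|---|---|---|---|
| mRNA dose | required, within 21 days | none in the window | no condition |
| Positive test | none within 8 weeks | required, within 8 weeks | no condition |

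**Inputs.** From the protocol: windows of 21 and 56 days, and 1,730 post-infection cases in the feasibility count (Section 9.5). Assumed, because the protocol does not give them: q, the share of Cohort 2 controls with a dose in the prior 8 weeks; p, the share ever vaccinated; and the distribution of a correlated factor.

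**1. Recent vaccination itself (8-week reading).** Exposure among cases is 0, so the odds ratio is 0 for any q > 0. Under no effect, the expected number of recently vaccinated cases is 1,730 × q, or 173 at q = 10% and 346 at q = 20%. The rule forces 0.

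**2. Ever vaccinated.** Case prevalence is (p − q)/(1 − q), so the odds ratio is (p − q)/p. At p = 50% this gives 0.90, 0.80 and 0.60 for q = 5%, 10% and 20%. If controls are screened the same way, it returns to 1.00.

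**3. A correlated factor with no true effect.** Suppose it is present in 40% of the recently vaccinated and 20% of others. Cases contain only the others, so their odds are 0.20/0.80 = 0.25. Control prevalence is 0.4q + 0.2(1 − q).

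| q | Control prevalence | Control odds | Crude OR |
|---|---|---|---|
| 10% | 0.22 | 0.282 | 0.89 |
| 20% | 0.24 | 0.316 | 0.79 |
| 30% | 0.26 | 0.351 | 0.71 |

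A factor less common among the recently vaccinated would be pushed above 1. This bias arises when recent vaccination is left out of the model. With it in, its coefficient diverges and the recently vaccinated controls in effect drop out.

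**4. Calendar time.** Cohort 2 starts on 01 January 2020 and the protocol's vaccination period on 11 December 2020. On the Figure 1 timeframe (to 01 November 2022) that is 345 of 1,035 days, one third, with no effect. If index dates were evenly spread and the 10%, 20% and 30% applied only to the later two thirds, the overall shares would be 6.7%, 13.3% and 20%, and the crude odds ratios 0.92, 0.85 and 0.79. The Cohort 1 mirror has no such unaffected period.

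**5. Does the window length matter?** On the 8-week reading, 56 − 21 = 35 of the 56 excluded days (62.5% of days, not of patients) lie beyond the Cohort 1 window. Shortening the exclusion to 21 days with controls unscreened leaves the odds ratio for a dose within 21 days at 0. For a dose within 8 weeks it gives 35/56 = 0.625, taking dose dates as uniform. Shortening alone does not remove the artefact.

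**The case against.** The strongest reply is that matching is left to the SAP, which may restrict or match controls on vaccination and infection. That is possible. But the protocol itself sets eligibility for both groups, conditions only the cases, and names neither exposure among its matching examples. Matching on the cohort-defining exposure alone would not cure it.

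A reader might infer that the study will report recent vaccination as protective in Cohort 2. The documents do not support that. The primary objective names demographics, medical history and comorbidities. No section says a vaccination odds ratio will be estimated in Cohort 2, and the exposure role in Table 1 may only mark the variables that define the cohorts. A factor with no exposed cases would also show up as separation rather than as a plausible estimate. The effect on correlated factors is less visible and does not need vaccination to be modelled.

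A reader might also take the 8-week exclusion, set against a 21-day vaccine window, as the error. It is not the cause. A longer washout gives a cleaner post-infection cohort, and 8 weeks for both competing exposures is defensible. Mutual exclusivity does not require it, however, since Cohort 1 already excludes a positive test within 8 weeks.

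Two further limits stand. The phrase in Cohort 2 can be read as the interval from positive test to diagnosis. The window is then usually shorter and the odds ratio for a dose anywhere in the 8 weeks need not be exactly 0, though screening stays one-sided. And the figures for correlated factors are crude, whereas Section 9.7 plans multivariable models that may absorb part of the bias.

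**Conclusion.** The point holds as an asymmetry in eligibility. Cases in Cohorts 1 and 2 are screened for the competing exposure and their controls, as the protocol is written, are not.

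The direct consequence is conditional: if the excluded exposure is modelled, its odds ratio in the excluded window is 0 by construction on the 8-week reading. The indirect consequence is bias in correlated factors. In the worked example this gives a crude odds ratio of 0.89 to 0.71 for a factor with no effect, at assumed control shares of 10% to 30%. It is milder if those shares apply only to the vaccine era, and absent from Cohort 2 before 11 December 2020. Both the shares and the 40% versus 20% split are assumptions, so the true size is unknown.

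On the 8-week reading, a test-positive case with a dose 22 to 56 days before diagnosis fits neither cohort. That is a loss of cases of unknown number, separate from the bias.

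**What to change.** In the control criteria of Section 9.2.1, add:

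- Cohort 2 controls have no mRNA COVID-19 vaccination record before index in the same window as their cases.
- Cohort 1 controls have no positive SARS-CoV-2 test on record within 8 weeks before index.

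In Section 9.7, state that recent vaccination is not estimated as a risk factor in Cohort 2, nor recent infection in Cohort 1. After equal screening neither contrast can be estimated.

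Clarify whether the Cohort 2 exclusion covers the full 8 weeks or only the time from positive test to diagnosis. If the latter, each control needs the matched case's interval counted back from its own index date.

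Keeping 8 weeks or using 21 days is a design choice, provided cases and controls share it. If 8 weeks stays, count the test-positive cases with a dose 22 to 56 days before diagnosis and add them in a sensitivity analysis, with controls screened to match.

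The cost is a few lines of protocol text, minor extra programming and a slightly smaller control pool, in a source of more than 106 million patients.
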